## 14.2.6 Selection Modeling

A selection model fits simultaneously a model for the repeated FEV1 measurements and a model for the probabilities of dropping out at the different visits. These models are referred to as the measurement model and the drop-out model.

Final Version 5.0 Page 45 of 76

Applying Diggle and Kenward's Selection Model on incomplete longitudinal data, the response is modeled through a repeated measures model, while a logistic regression model is used to describe the dependency of the missing data indicators on the longitudinal responses.

Under this approach, the probability of dropout is considered a function of the observed longitudinal response measured prior to dropout at time j and the unobserved response at the time of dropout. For individuals with complete data, dropout depends on the response prior to the last measurement  $(y_{i,j-1})$  and the final observed response  $(y_{ij})$ . In either case, dropout cannot depend on future responses. Specifically, the logit of the probability of dropout depends on the observation prior to dropout  $(y_{i,j-1})$  (assuming the individual was observed prior to dropout) and the unobserved response at dropout  $(y_{ij})$ :

Logit[
$$P(Di=j|Di>=j] = Intercept + \alpha_1 y_{i,j-1} + \alpha_2 y_{ij}$$

where the coefficients  $\alpha_1$  and  $\alpha_2$  are the effects of  $y_{i,j-1}$  and  $y_{ij}$  on the logit, respectively. Under this model, if both  $\alpha_1$  and  $\alpha_2$  are equal to zero, then the missingness is independent of the previous and missing responses. In such cases, the missing data are Missing Completely at Random, and consequently, the missing data process is ignorable. If  $\alpha_2$  but not  $\alpha_1$  is equal to zero, then the missingness is related to the response prior to dropout. In this case, the missing data are MAR, and again, the missing data process is ignorable. If  $\alpha_2$  is not equal to zero, then the missingness depends on the missing data at dropout. Consequently, the missing data process cannot be ignored.

These scenarios will describe how large the departure from the MAR assumption should be in order to substantially affect the results of the primary analysis. If the number of drop-outs turns out to be small, this sensitivity analysis may not be feasible because of insufficient information to fit the logistic drop-out model, and the CSR will mention this as a caution. This model can be fitted using the selection modelling macros from the Drug Information Association Scientific Working Group on Estimands and Missing Data [8].

## 14.2.7 Joint Model

This analysis jointly models the repeated FEV1 measurements and the time to dropout. The longitudinal measurement process model follows a standard random-coefficient mixed effect model, while the dropout mechanism model uses a complementary log-log link.

This model will be fitted using the shared parameters macros from the Drug Information Association Scientific Working Group on Estimands and Missing Data [8].

## 14.3 Supplementary Analyses for the Primary Endpoint

Supplementary analyses can provide additional insights into the understanding of a treatment effect.

Final Version 5.0 Page 46 of 76

#### 14.3.1 PPS

The population for the primary estimand will be altered from the FAS to the PPS. The analysis will be conducted as described for the primary endpoint.

### 14.3.2 **CC** data

The endpoint for the estimand will be spirometry data stored on the conducted as described for the primary endpoint.

### 14.3.3 The impact of COVID-19

The COVID-19 pandemic has impacted the conduct of the study and might have impacted its results for different aspects including infections, quarantines, social distances [5], and other considerations linked to the different ways that each site has faced the pandemic. Date of COVID-19 outbreak was set at March 11, 2020 and different analyses will be performed to assess the impact of the COVID-19 pandemic to the study pre and post pandemic. In case evidence of an impact of pandemic on study endpoints should emerge, considerations on how the initial study assumptions have been altered must be done, and changes in the statistical criteria for final judgment should be applied.

### 14.3.3.1 Patients impacted by COVID-19 pandemic

The analysis of primary endpoint will be performed using the LMM described in the primary analysis with the inclusion of additional categorical covariates:

- A binary covariate representing if patients have been affected by COVID-19 during the treatment period:
  - Affected, if an AE of COVID-19 is reported in the eCRF AE page between randomization and end of treatment date;
  - Not affected, if no AEs of COVID-19 are reported in the eCRF AE page between randomization and end of treatment date.
- A binary covariate representing if patients have been randomized before or after the COVID-19 pandemic outbreak:
  - Before, if date of randomization is before 11 March 2020;
  - After, if date of randomization is equal or after 11 March 2020.

FEV1 data will be descriptively summarized by impact of COVID-19 (COVID-19 affected vs Not COVID-19 affected, and randomized before COVID-19 Pandemic Outbreak vs randomized after COVID-19 outbreak) at each visit, by treatment and overall. The treatment comparison for difference in mean change from baseline in the FEV1 at week 48 will be carried out using t-tests as described in section 14.3.4. This will also be performed for each of the subpopulations defined

Final Version 5.0 Page 47 of 76

by the binary covariates above i.e. patients affected/not affected by COVID-19 during the treatment period and patients randomized before/after the COVID-19 pandemic outbreak.

Furthermore, it is of interest to categorize each visit for each patient to assign these before or after the COVID-19 pandemic outbreak. A summary table will be produced to descriptively display the effects of FEV1 over time by taking each visit with respect to the COVID-19 outbreak pandemic date into consideration. The treatment comparison for difference in mean change from baseline in the FEV1 at week 48 will be analyzed similarly using the t-test as described in section 14.3 for both groups, visits before COVID-19 pandemic outbreak, visits after COVID-19 pandemic outbreak.

The observed mean change from baseline and standard errors of FEV1 at each timepoint will be graphically reported by treatment and by impact of COVID-19 categorization. This will also be displayed by COVID-19 pandemic outbreak at each visit. Furthermore, a figure with adjusted mean changes from baseline at each visit by treatment group derived from the LMM with impact of COVID-19 will be provided.

### 14.3.3.2 Piecewise regression

The analysis of primary endpoint will be carried out using a modified LMM for repeated measurements that will allow to assess if FEV1 trajectory slopes are different before and after the COVID pandemic outbreak. All observed available FEV1 measurements will be used and the model will contain (except from the intercept) time (from randomization), time after COVID pandemic outbreak (defined as days after March 11, 2020, with March 11, 2020 considered as equal to zero; for assessments of FEV1 done before 11 March 2020 this time is set at zero), treatment, the interactions of time (from randomization) by treatment, the interactions of time after COVID pandemic outbreak by treatment, baseline FEV1, the interactions of time (from randomization) with the baseline FEV1, the interactions of time after COVID pandemic outbreak with the baseline FEV1, region (North America versus all other countries together), age (< 55 versus □ 55 years), and use of azithromycin at randomization (i.e. Baseline, Visit 1). The model will include random intercept, time and time after COVID pandemic outbreak.

Denoting the time from randomization and the time after COVID pandemic outbreak by  $S_1$  and  $S_2$  respectively, treatment group by T (0=SoC; 1=L-CsA plus SoC), the day of the measurement by t and the baseline FEV1 by X, the fixed part of the model will contain the following covariates:

Intercept, S1, S2, T, T\*S1, T\*S2, X, X\*S1, X\*S2, other covariates.

The Kenward-Roger adjustment will be used for the denominator degrees of freedom needed for hypothesis tests and confidence intervals.

The primary efficacy parameter will be estimated from the model by the adjusted difference between treatment groups in mean FEV1 change from baseline after 48 weeks. The p-value for the null hypothesis of no difference and a two-sided 95% confidence interval for the difference will

Final Version 5.0 Page 48 of 76

be provided. Superiority of L-CsA will be confirmed by a statistically significant result in favor of the L-CsA plus SoC treatment compared to SoC alone.

The slopes of FEV1 before and after March 11, 2020 will be assessed and compared.

The core excerpt of cole code for the primary analysis is reported in section 17.5.

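### The COVID-19 piecewise regression counts time after the outbreak in calendar days for every patient, which pulls its slope-change estimate strongly towards zero

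*SAP*

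**What the plan says.** The model in SAP 14.3.3.2 is meant to "allow to assess if FEV1 trajectory slopes are different before and after the COVID pandemic outbreak". It has two time variables: S1, time from randomization, and S2, "time after COVID pandemic outbreak (defined as days after March 11, 2020, with March 11, 2020 considered as equal to zero". The only adjustment to S2 is that "for assessments of FEV1 done before 11 March 2020 this time is set at zero".

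S2 enters as a main effect, in interactions with treatment (T) and with baseline FEV1 (X), and at patient level: "The model will include random intercept, time and time after COVID pandemic outbreak".

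The model has two outputs. The slopes "before and after March 11, 2020 will be assessed and compared". Also, "The primary efficacy parameter will be estimated from the model by the adjusted difference" between arms after 48 weeks, and the section says a significant result would confirm superiority. It gives no S2 value for that contrast.

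Patients randomized after the outbreak are expected; SAP 14.3.3.1 defines the group as "After, if date of randomization is equal or after 11 March 2020". The parent section, 14.3.3, says that if evidence of a pandemic effect on the endpoints emerges, "changes in the statistical criteria for final judgment should be applied".

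**The concern.** A piecewise model needs its second time variable to start at zero at the break, or at entry for a patient who enters after the break. Calendar days do this only for patients already on study on 11 March 2020. A later patient arrives with S2 already in the hundreds of days. Because the outcome is change from baseline (SAP 14.1.3), it is near zero at entry whatever the date. The fit can reconcile the two only by shrinking the S2 coefficient.

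At stake is the one analysis built to estimate a slope break. A real change could be reported as a tight near-null, in a section where evidence of pandemic impact is meant to influence how the trial is judged.

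**Working it through.** SAP 14.3.3.2 states no figure, so there is none to reproduce.

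**1. Algebra.** Take a control patient randomized d days after 11 March 2020. To within the one day that SAP 9.3 adds to time from randomization, S2 = S1 + d. With other covariates fixed:

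- predicted change = b0 + b1·S1 + b2·(S1 + d) = (b0 + b2·d) + (b1 + b2)·S1;
- on day 0 this is b0 + b2·d, although the observed change is near 0.

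The T and X interactions with S2 carry the same offset, and the random S2 effect implies day-0 spread that grows with d. For a patient randomized before the outbreak, S2 is zero and then counts days on study since the outbreak, which is correct.

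**2. Size of the misfit.** Assume a true slope change of 0.4 mL/day. The implied day-0 offset is 0.4 × 386 = 154 mL at d = 386 and 0.4 × 1141 = 456 mL at d = 1141. The planned treatment effect is 200 mL (SAP 8.2).

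**3. Patients affected.** The interim cutoff was 30 September 2021, 568 days after the outbreak. Week 24 is 168 days, with a 14-day visit window. Patients not yet at Week 24 by the cutoff were therefore randomized about 568 − 168 = 400 days after the outbreak (386 to 414) or later. Everyone randomized before the outbreak had passed Week 24 or discontinued by then. The interim set was planned at about 54 and 169 were randomized (SAP 8.3, 8.2), so roughly 54/169 = 32% at most are pre-outbreak. The other 115 (68%) have d near 400 or more. The actual interim size is not visible.

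**4. Expected estimates (generalised least squares at the scheduled visits).** Assumptions:

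- control slope −0.9 mL/day before the outbreak, changing by +0.4; treatment effect on slope +0.3, plus another +0.3 after the outbreak;
- SDs: intercept 30 to 200 mL, slope 0.9 mL/day, residual 100 mL;
- 17, 34 or 54 patients pre-outbreak, the rest enrolled from day 386 to day 900 or 1141.

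| Quantity (mL/day) | True | Calendar S2 | On-study S2 |
|---|---|---|---|
| b2, slope change | 0.400 | 0.018 to 0.047 | 0.400 |
| T×S2 | 0.300 | 0.021 to 0.036 | 0.300 |
| b1 + b2, slope after | −0.500 | −0.511 to −0.558 | not tabulated |

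Calendar coding recovers 5-12% of the slope change, and 2-12% on a wider grid (10-30% pre-outbreak, delays from 100 days). The slope after the outbreak is roughly right; the error falls on the slope before it. With 17 pre-outbreak, for example, b1 = −0.511 − 0.023 = −0.534 against a true −0.900.

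**5. Precision.** In 60 simulated trials of 168 patients (25% pre-outbreak, the rest 6 to 36 months after; decline 300 mL/year before, 100 after), the true change was +200 mL/year.

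- Calendar S2: +9, SE 13. The interval 9 ± 1.96 × 13 runs from −16 to +34.
- On-study S2: +198, SE 94. The interval 198 ± 1.96 × 94 runs from +14 to +382.

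A small REML check (16 runs, 54 pre-outbreak, some convergence warnings) agreed: mean b2 was 0.021 (SD 0.025) with calendar S2 and 0.52 (SD 0.30) with on-study S2, against 0.400.

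**6. Week 48 treatment difference.** In the 60-trial simulation it was 185 mL with one coding and 182 mL with the other. When the treatment effect on slope was assumed to grow after the outbreak (true difference 202 mL for later patients), the calendar-coded contrast was 136-181 mL at S2 = 0, 171-196 at S2 = 836 and 183-220 at S2 = 1336.

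**7. Is recoding enough?** With on-study S2, every patient randomized after the outbreak has S2 = S1, so b2 also absorbs slope differences between cohorts. With no within-patient change and a pure cohort slope difference of 200 mL/year, the recoded model reported 181-201 mL/year in one check and about 117-172 in another with different assumptions. Adding a before/after indicator and its interaction with S1 removed this.

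**The case against.** The best defence is that little depends on this model. SAP 14.3 is supplementary. The primary model uses time from randomization only. SAP 14.3.3.1 and 14.3.3.3 examine COVID-19 in other ways: a before/after covariate in the primary model, t-tests by cohort and by visit timing, and a while-on-treatment analysis. None of them uses S2. The code in SAP 17.5 and the variable descriptions are withheld and may already reset S2, and the enrolment halt and restart dates are redacted.

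Most of this stands, and it rules out several stronger readings that a reader might infer:

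- *The slope change cannot be estimated.* It is biased, not unidentifiable. If all 169 patients had been randomized before the outbreak, or if patient intercepts were left effectively free, the calendar coding would recover it in full.
- *This analysis decides whether the pandemic mattered.* SAP 14.3.3 announces several analyses and names no deciding one.
- *The efficacy result is compromised.* The primary test is untouched, and the Week 48 difference barely moved in the 60-trial simulation.
- *The report is bound to show no slope change.* That depends on enrolment timing, which the documents do not give.

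The defence does not remove the fault. The SAP's definition is explicit, and hidden code cannot make it correct. The other COVID-19 analyses do not estimate a slope break.

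**Conclusion.** The definition of S2 does not serve the model's stated aim. For patients randomized after the outbreak, probably about two thirds or more of the trial, it ties change from baseline on day 0 to enrolment date. The slope-change coefficient is then strongly attenuated, to about 2-12% of its true value, with an interval far too narrow.

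The direction follows from the algebra. The percentages rest on assumed slopes, variances and enrolment dates, and the two-thirds share rests on the planned interim size. The effect on the Week 48 contrast was small in the 60-trial simulation but depends on an S2 value that the SAP does not state. This is a correctable fault in a supplementary analysis. It deserves correction because a falsely precise near-null could enter the judgement that SAP 14.3.3 calls for.

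**What to change.** Amend SAP 14.3.3.2 before unblinding:

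1. Define S2 as days on study after the outbreak: max(0, visit date − the later of randomization date and 11 March 2020).
2. Add the randomized-before/after indicator from SAP 14.3.3.1 and its interaction with S1, so that b2 rests on within-patient change in patients who span the outbreak. The indicator alone does not remove a cohort difference in slope. If T×S2 is to be read in the same within-patient way, it needs the matching interactions with treatment.
3. State the S2 value for the Week 48 contrast. This matters after recoding too: under the slopes assumed above, the difference is 0.3 × 336 = 101 mL at S2 = 0 and (0.3 + 0.3) × 336 = 202 mL at S2 = 336.
4. Check that the SAP 17.5 code matches.

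This takes a few SAP sentences and minor derivation code, with no new data. The drawback is precision. The SE of b2 was about 0.26-0.47 mL/day with on-study S2 alone, against a true 0.400. The added terms widen it further, because only patients on study across the outbreak then inform it. The report should say so, and should not read a non-significant slope change as absence of an effect.

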### 14.3.3.3 "While on treatment" strategy (for COVID-19)

A further supplementary analysis on the impact of COVID-19 will be performed. The IE of COVID-19 infection (per eCRF page, see definition in section 14.3.3.1) will be considered and will be handled by the "while on treatment" strategy: the analysis will be conducted as the primary analysis with the exception that, in case of a COVID-19 IEs, only the FEV1 measurements up to the date the COVID-19 AE started will be used.

In case re-transplantation events, FEV1 will be imputed as zero at each nominal day post event up to the COVID-19 infection date. According Table 5, in case of death, no imputation will be done.

#### 14.3.4 T-test

The population-level summary for the variable will be altered. The mean treatment difference in change from baseline to Week 48 in FEV1, standard deviation and 95% confidence interval will be presented. A two-sample t-test will be performed by treatment group using change from baseline in FEV1 to Week 48.

In case of death or re-transplantation events, FEV1 will be imputed as zero at each nominal day post event.

## 14.3.5 "While on treatment" strategy"

The IE discontinuation of randomized treatment will be considered and treated following a while on treatment strategy. In case of such IE, all FEV1 measurements up to the date of the IE will be included, while the observation post IE will not be considered. The analysis will be conducted as described for the primary endpoint (section 14.1).

As an additional analysis, the initiation of additional immunosuppressive therapy (see section 14.5.1 for details on additional immunosuppressive therapies) will be included in the analysis: IEs of either discontinuation of randomized treatment or initiation of additional immunosuppressive therapy will be analyzed according to the above while on treatment strategy.

In both analyses, the summary statistics of time to treatment discontinuation (weeks) and time to initiation of additional immunosuppressive therapy (weeks) (for the second analysis only) will be provided for a better interpretation of results.

In case of re-transplantation events, FEV1 will be imputed as zero at each nominal day post event. According Table 5, in case of death, no imputation will be done.

Final Version 5.0 Page 49 of 76

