#### 12.1.4 Re-transplantation

Re-transplantation is defined as the date that a patient undergoes lung re-transplantation surgery. The reason for re-transplantation will be recorded. At the time of re-transplantation, the patient will be withdrawn from the study.

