### 8.2 Sample Size Considerations

The initial sample size was based on the following considerations. Assuming a treatment group difference for mean FEV1 change from baseline of 200 mL (0.2 L) and a standard deviation of 350 mL (0.35 L) at the end of treatment Week 48, an independent samples t-test with a one-sided type I error level of  $\alpha$ =0.025 will have at least 80% power to reject the null hypothesis when the sample size in each treatment group is at least 50 patients. To compensate for a loss of power due to premature withdrawals, a total of 110 patients will initially be randomized.

An interim analysis (IA) was performed to re-assess sample size and delivered to the Sponsor on December 1st, 2021. Results of the IA are presented in a separate IA report (section 19.1).

It was anticipated that approximately 160-170 patients have been randomized in BOSTON-2 and approximately 60 patients in BOSTON-1. 169 patients were actually randomized in BOSTON-2 and 62 patients in BOSTON-1.

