### 14.1.3 Analysis Model

The primary efficacy analysis will be carried out using a LMM for repeated measurements, using all observed available  $FEV_1$  measurements. In case of death or re-transplantation events,  $FEV_1$  will be imputed as zero at each nominal day post event.

The dependent variables are the absolute change from baseline of FEV1 measurements at visit 2 (i.e., the first post-baseline visit) through visit 9 (Week 48). For the definition of baseline FEV1 please refer to section 8.1.1.

A flexible and robust model will be chosen for the random part of the LMM according to a prespecified stepwise procedure (see next section). The fixed part of the LMM is specified as follows: the model will contain (except from the intercept) time cubic splines, treatment, the interactions of time splines by treatment, baseline FEV1, the interactions of time splines with the baseline FEV1, region (North America versus all other countries together), age (< 55 versus  $\ge 55$  years), and use of azithromycin at randomization (i.e. Baseline, Visit 1).

The primary efficacy parameter will be estimated from the model by the adjusted difference between treatment groups in mean FEV1 change from baseline after 48 weeks. The p-value for the null hypothesis of no difference and a two-sided 95% confidence interval for the difference will be provided.

Superiority of L-CsA will be demonstrated by a statistically significant result (defined as p<0.025, one-sided) in favor of the L-CsA plus SoC treatment compared to SoC alone.

The above comparison between treatment groups at all the other visits (2-8) will also be presented.

A figure of observed mean change from baseline and standard errors at each visit, by treatment group will be presented. A figure with adjusted mean changes from baseline at each visit by treatment group derived from the LMM will be provided.

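### The COVID-19 while-on-treatment analysis (SAP 14.3.3.3) also drops the primary's zero for death, so a shift from the primary cannot be attributed to COVID-19; 14.3.5 shares the death/re-transplantation split and reports a hypothetical-type Week 48 contrast

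*SAP*

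**What the plan says.** **Primary analysis (SAP 14.1.1, 14.1.3).** Death and re-transplantation are both scored as FEV1 of zero at later nominal days. The parameter is the adjusted between-group difference in mean change at Week 48 from the linear mixed model (LMM), tested at a level "defined as p<0.025, one-sided". SAP 9.5.1 states that missing data in this model are taken as missing at random (MAR).

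**COVID-19 version (SAP 14.3.3.3).** The text says "the analysis will be conducted as the primary analysis with the exception that, in case of a COVID-19 IEs", only FEV1 up to the start of the COVID-19 adverse event is used. Re-transplantation scores zero up to the infection date. Death is not imputed. Table 5 marks death as not applicable in this column, and keeps FEV1 collected after treatment discontinuation.

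**General version (SAP 14.3.5).** FEV1 after stopping randomized treatment is dropped; a second run also drops FEV1 after additional immunosuppression. The model is the one for the primary endpoint. Re-transplantation scores zero, but "According Table 5, in case of death, no imputation will be done". Table 5 agrees.

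No reason is given for separating the two events. Re-transplantation ends observation as death does: under Protocol 12.1.4, "At the time of re-transplantation, the patient will be withdrawn from the study".

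**The concern.** An analysis meant to isolate one intercurrent event should differ from the primary only in how that event is handled. Section 14.3.3.3 does not: it also removes the zero for every death, including deaths in patients who never had COVID-19. If deaths are unevenly split between arms, the estimate moves for a reason unrelated to the pandemic. SAP 14.3.3 says that evidence of a pandemic effect on endpoints should lead to altered statistical criteria for the final judgment, so a shift produced by death handling could be taken for such evidence.

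In 14.3.5 the issue is mainly what is estimated. A while-on-treatment estimand summarizes response up to the intercurrent event. This analysis discards later data and then asks the LMM for a Week 48 contrast, which for patients who died or stopped describes what would have happened had they continued. The zeros for re-transplantation add a composite element, and no rule covers re-transplantation after treatment has stopped.

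**Working it through.** **1. The design figure.** SAP 8.2 assumes a 200 mL difference, "a standard deviation of 350 mL (0.35 L) at the end of treatment Week 48" and one-sided alpha 0.025, and states that the t-test "will have at least 80% power to reject the null hypothesis when the sample size in each treatment group is at least 50 patients". By normal approximation, n = 2 × (1.960 + 0.842)² × (350/200)² = 48.1, so 49 per group. The exact noncentral t gives power 0.7996 at 49 and 0.8076 at 50, so 50 is reproduced. The 200 mL serves below only as a yardstick. The plan states no figure for these two analyses.

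**2. The rules side by side.**

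| Event | Primary | 14.3.3.3 | 14.3.5 |
|---|---|---|---|
| Death | zero | not imputed | not imputed |
| Re-transplantation | zero | zero, up to COVID-19 onset | zero |
| FEV1 after stopping treatment | used | used | dropped |
| FEV1 after COVID-19 onset | used | dropped | used |
| Parameter | Week 48 contrast | Week 48 contrast | Week 48 contrast |

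From the primary to 14.3.3.3, the death row changes as well as the COVID-19 row.

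**3. What happens to an unimputed death.** Table 5's MAR row names residual missing data, consent withdrawal and loss to follow-up, not death, so this step is an inference. No other rule is given, however. Protocol 15.2.3.1 took values missing through death as MAR and modelled FEV1 to Week 48 as if the event had not occurred. SAP 14.3.6 likewise describes the LMM as implicitly modelling Week 48 FEV1 for patients who died.

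**4. Size of the death rule.** Inputs: 169 randomized (SAP 8.2), so 169/2 = 84.5 per arm. Assumptions, because the documents give neither value: mean baseline FEV1 B = 1.5, 2.0 or 2.5 L, and a modelled Week 48 change of −0.3 L for a patient who died. Replacing the zero by the model's prediction changes that patient's value by B − 0.3 L. For an imbalance of k deaths, shift = k × (B − 0.3)/84.5:

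| Imbalance | B = 1.5 L | B = 2.0 L | B = 2.5 L |
|---|---|---|---|
| 1 death | 14.2 mL | 20.1 mL | 26.0 mL |
| 3 deaths | 42.6 mL | 60.4 mL | 78.1 mL |
| 5 percentage points (0.05 × 84.5 = 4.2 deaths) | 60 mL | 85 mL | 110 mL |

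The last row is 0.05 × 1.2, 1.7 and 2.2 L.

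**5. Size of the label problem in 14.3.5.** Assume linear decline to −100 mL (L-CsA) and −300 mL (SoC) at Week 48, with a fraction q of L-CsA patients stopping at week t. The Week 48 MAR target is 200 mL throughout. Response up to stopping gives 300 − 100 × [(1 − q) + q × t/48]:

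- q = 0.1, t = 36: 300 − 97.5 = 202.5 mL
- q = 0.3, t = 12: 300 − 77.5 = 222.5 mL

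A simulation of 150 trials used 84 patients per arm, 20% of L-CsA patients stopping and 5% of each arm dying at Week 24, and a simplified random-intercept and random-slope model without imputation. The Week 48 contrast averaged 197 mL (simulation SE 4), consistent with the 200 mL value for no stopping and no death. The difference at last on-treatment value averaged 201 mL (SE 4; expected 204.5). The model thus targets the hypothetical quantity, but the numerical gap was small here.

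**The case against.** **The death rule is disclosed.** A reader might infer that 14.3.3.3 conceals a second change. It does not: the same section says that death is not imputed and cites Table 5. What remains is that two changes are made together in a run introduced as having one exception.

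**Leaving death unimputed can be defended.** Nothing exists on treatment after death, and Protocol section 5 (Statistical Considerations) restricts this estimand to on-treatment measurements. That stands for 14.3.5 taken alone. It does not explain zeros for re-transplantation, or a Week 48 parameter.

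**Off-treatment patients are not extrapolated in both analyses.** A reader might infer that they are. Table 5 keeps off-treatment FEV1 in the COVID-19 version; there it is patients after COVID-19 onset whose course is extrapolated. Off-treatment data are dropped only in 14.3.5.

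**Other COVID-19 analyses exist.** SAP 14.3.3.1 adds COVID-19 covariates to the primary LMM without changing its death rule, and 14.3.3.2 compares slopes before and after the outbreak. Conclusions about the pandemic need not rest on 14.3.3.3. This lowers the stakes but does not make that run interpretable.

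**The events may be few.** Protocol 15.2.3.1 expects death, re-transplantation and consent withdrawal to be rare. If deaths are few or balanced, the shift is small.

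**Conclusion.** The inconsistency is real and confined to supplementary analyses. As specified, a difference between 14.3.3.3 and the primary cannot be assigned to COVID-19, because the zero for death goes too. Section 14.3.5 mixes a zero for re-transplantation, no value for death and a Week 48 MAR contrast, so its result is a hypothetical-type estimate with a composite element.

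The death rule is worth about 14 to 26 mL per one-death imbalance, or 60 to 110 mL for a 5-point imbalance, against the 200 mL design effect, and little if deaths are balanced. This rests on the assumed baseline FEV1 and 0.3 L decline, and the actual imbalance is unknown. Multiplying 5 points by the whole baseline gives 75 to 125 mL, but that is a gross figure: it ignores the FEV1 decline the model would predict. The label problem was smaller, reaching about 22 mL in the most extreme case tried.

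A reader might infer that the primary conclusion is at risk. The documents do not support that: neither analysis enters the primary test, and its type I error is unaffected.

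**What to change.** **SAP 14.3.3.3 and its Table 5 column.** Apply the primary rule, FEV1 of zero at post-event nominal days, to death as well as re-transplantation unless COVID-19 onset came first. Replace the not-applicable entry for death. Only COVID-19 handling then differs from the primary.

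**SAP 14.3.5 and its Table 5 column.** Label the Week 48 MAR result hypothetical, or add a summary up to the intercurrent event, such as the last on-treatment change. State one justified rule for death and re-transplantation. Do not copy the ordering rule here with treatment discontinuation in place of COVID-19. Under SAP 15.2.2 the L-CsA period ends at the last dose, whereas the SoC period runs to study completion or early termination. An L-CsA patient who stopped inhaling and later died would escape the zero, while a SoC patient who died would have no comparable earlier stop. That would favour L-CsA.

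**Cost.** Wording in two sections and Table 5, and a small data-step change. The estimates may move closer to the primary.
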